6.10. Concomitant Medications and Non-Drug Therapies

All medications taken at any time from 3 months prior to screening to the follow-up visit will be recorded in the eCRF. The minimum requirement is that drug name and the dates of administration are to be recorded.

Subjects on OAM at screening must discontinue OAM treatment as instructed in the protocol (see Section 4). After the last dose of albiglutide or exenatide, the investigator will provide subjects who were previously on an OAM with instructions of how and when to restart his/her OAM. The half-life of his/her study treatment (albiglutide/exenatide) should be taken into consideration (see Section 6.9).

6.10.1. Permitted Medications and Non-Drug Therapies

Unless specified as a prohibited medication in Section 6.10.2, all concomitant prescription or over the counter medications should be considered permitted provided they are not contraindicated in the albiglutide or exenatide (depending on study treatment) PI or for the individual subject concerned. Although stable doses of all concomitant medications are preferable, changes in medications during the study to appropriately treat clinical conditions that might arise are allowed.

Like other members of the class, albiglutide and exenatide cause a delay in gastric emptying, and thereby have the potential to impact the absorption of concomitantly administered oral medications. This should be taken into account by investigators when prescribing concomitant medication.

Investigators must adhere to the US FDA-approved PI for all permitted medications.

6.10.2. Prohibited Medications and Non-Drug Therapies

Subjects must not use any of the following medications during the study (screening to end of treatment):

- Any antidiabetic medications (e.g., GLP-1R agonist, DPP-4 inhibitors, metformin, meglitinide, sulphonylurea, thiazolidinedione, SGLT2 inhibitors or insulin) other than the randomly assigned study treatment.
- Any investigational drug other than the study treatment they have been randomly assigned to.

- Oral or systemically injected corticosteroids (inhaled, intra-articular, epidural, and topical corticosteroids are allowed); short courses of oral steroids (single dose or multiple doses for up to 7 days) may be permitted provided these cases are discussed with the Medical Monitor.
- Antiretroviral drugs.
- Prescription and over-the-counter weight loss drugs.
- Any subject requiring medications that may produce or reduce nausea or significantly affect gastrointestinal motility such as prokinetics (e.g., erythromycin), anti-emetics (e.g., metoclopramide), narcotic analgesics (e.g., morphine), anticholinergics (e.g., domperidone), anti-acids (e.g., over the counter antacids, proton pump inhibitors, H2 blockers), laxatives and drugs affecting pancreatic or hepatobiliary systems.

If a subject receives a prohibited medication, the investigator should make the evaluation based on the reason (i.e., AE), duration of exposure and timings relative to the assessments in consultation with the Medical Monitor.

7. STUDY ASSESSMENTS AND PROCEDURES

Protocol waivers or exemptions are not allowed with the exception of immediate safety concerns. Therefore, adherence to the study design requirements, including those specified in the Time and Events Table, are essential and required for study conduct.

This section lists the procedures and parameters of each planned study assessment. The exact timing of each assessment is listed in the Time and Events Table Section [7.1](#).

7.1. Time and Events Table

Table 2 Time and Events Table - Study Part A

Procedures	Screening/Wash-Out Period (0-3 Weeks)			Treatment Period (exenatide) (5 Days)					Un-scheduled	Early Withdrawal	Follow Up Within 7 Days
	-21 to Day -4	Day -3 to -5	Day -1 ¹³	Day 1	Day 2	Day 3	Day 4 ± 1 day ¹³	Day 5 ± 1 day ¹³			
Study Visit	1		2	3			4	5			6
Informed consent	X										
Inclusion and exclusion criteria	X		X ¹								
Demography, medical/disease history	X										
Enrolment into Treatment Phase				X							
OAM washout ²		X									
GEBT ³			X					X ¹²			
EGG /water load / VAS ³				X ¹¹			X ¹²				
ECG	X										
Vital Signs	X		X	X			X	X		X	X
Height, Weight, BMI	X										
Physical exam (F, Full; B, Brief) ⁴	F							B		B	
Concomitant medications review	X		X	X			X		X	X	X
AEs, SAEs, AEs of special interest review	X ⁵		X ⁵	X			X	X	X	X	X
PAGI-SYM ⁶	X										
GCSI-DD			X	X			X	X			
Chemistry, hematology, urinalysis, lipids ⁷	X							X		X	
HbA _{1c}	X										
FPG	X		X	X			X	X	X	X	X
Fasting capillary glucose at clinic ⁸			X	X			X	X			
Diet/Exercise/SMBG advice/reinforcement ⁹	X	X						X	X	X	X
Estradiol and FSH (females only: if required)	X										
Serum/Urine pregnancy test (FRP only)	S		U					U		U	U
TSH, Amylase and lipase	X										
Genetics sample ¹⁰				X							
RAMOS registration				X					X	X	

Procedures	Screening/Wash-Out Period (0-3 Weeks)			Treatment Period (exenatide) (5 Days)					Un-scheduled	Early Withdrawal	Follow Up Within 7 Days
	-21 to Day -4	Day -3 to -5	Day -1 ¹³	Day 1	Day 2	Day 3	Day 4 ± 1 day ¹³	Day 5 ± 1 day ¹³			
Study Visit	1		2	3			4	5			6
Exenatide dosing				X ¹¹	X	X	X ¹²	X ¹²			
Study medication compliance				X			X	X			

1. **Before baseline assessment (Day -1)**, the investigator must review **all** inclusion and exclusion criteria to confirm subject's eligibility. If a subject no longer meets all of the eligibility criteria, **do not administer the study treatment** and contact the Medical Monitor to discuss how to proceed (e.g., to determine if repeat testing is warranted).
2. For subjects taking OAM at screening only. At a minimum, two day washout for immediate release and at minimum 4 day washout for extended release OAMs. See footnote 13. For information on restarting OAM refer to Section 6.9.
3. A small meal will be provided 2 hrs prior to the EGG procedure (Section 7.3.1). A meal will also be provided post-procedure for both the EGG and GEBT.
4. Details of full and brief physical examinations are provided in Section 7.4.3.
5. SAEs related to study participation only.
6. The GCSI-DD questionnaire will be completed after the standard AE questions have been answered.
7. Clinical chemistry, hematology, urinalysis and lipid assessments are described in Section 7.4.6. Lipids will be assessed at screening only.
8. Fasting capillary glucose will be measured prior to administration of exenatide. On GEBT (Day 5) or EGG (Day 1 and Day 4) assessment days, fasting capillary glucose will be measured prior to the GEBT or EGG procedure.
9. Subjects will be provided with diet and exercise guidance (see Section 7.4.8) and instructed on self monitoring blood glucose at screening (See Section 7.4.9). Subject will be instructed to bring in their glucometers at each visit for review. Diet/exercise/SMBG reinforced at subsequent visits.
10. Informed consent for optional genetic research should be obtained before collecting a sample.
11. On the morning of Day 1, subjects will receive instructions and training on exenatide self administration and will be monitored by medical staff at the clinic during administration of the first dose. The first dose of exenatide will be administered after the baseline EGG procedure and before the post-procedure meal.
12. On Day 4 and 5, the morning dose of exenatide will be administered at clinic 1 hr (± 15 min) before the EGG or GEBT procedure.
13. Every effort should be made to schedule the procedures on the nominal visit day identified. However, in order to meet scheduling needs, subjects taking OAM can schedule Day-1 up to 3 days prior to Day 1 and the OAM stopped at least the day before the GEBT . For subjects treated with diet and exercise alone Day-1 can occur within 7 days prior to Day 1. The EGG and GEBT should not be scheduled on the same day

Table 3 Time and Events Table Study Part B

Procedures	Screening/Wash-Out Period (0-3 weeks)		Treatment Period (exenatide or albiglutide) (8 weeks)										Un scheduled	Early Withdrawal	Follow-Up
	-3 to -1	-1 ¹⁶	1	2 ¹⁶	3	4	5 ¹⁶			6	7	8 ¹⁶			
Study Week	-3 to -1	-1 ¹⁶	1	2 ¹⁶	3	4	5 ¹⁶	6	7	8 ¹⁶	12				
Study Day	-21 to -4	-3 to -5	-1	1	10±1	-	-	29±1	31±1	32±1	-	-	52±1	53±1	
Study Visits	1		2	3	4			5	6	7			8	9	10
Informed consent	X														
Inclusion and exclusion criteria	X		X ¹												
Demography, medical/disease history	X														
RAMOS registration			X				X						X	X	
OAM washout ²		X													
GEBT ³			X							X ⁵			X ⁵		
EGG /water load / VAS ³				X ⁴	X ⁵			X ⁵				X ⁵			
ECG	X														
Vital Signs	X		X	X	X			X	X			X	X	X	X
Height, Weight, BMI	X											X ⁶		X ⁶	
Physical exam (F, Full; B, Brief) ⁷	F											B	B	B	B
Concomitant medications review	X		X	X	X			X	X	X		X	X	X	X
AEs, SAEs, AEs of special interest review	X ⁸		X ⁸	X	X			X	X	X		X	X	X	X
PAGI-SYM	X														
GCSI-DD ⁹			X	X	X			X	X			X	X		
Chemistry, hematology, urinalysis, lipids ¹⁰	X							X ¹¹				X		X	
HbA1c	X			X				X				X		X	
FPG	X		X	X	X			X	X	X		X	X	X	
Diet/Exercise/SMBG advice/reinforcement ¹²	X		X	X	X			X				X	X	X	X
capillary blood glucose at clinic			X	X	X			X	X	X		X	X	X	X
Estradiol and FSH (females only: if required)	X														
Serum/Urine pregnancy test (FRP only)	S			U			U					U		U	U
TSH, Amylase and lipase	X														
Genetics sample ¹³				X											
Randomization				X											
Dispense study medication			X				X								

Procedures	Screening/Wash-Out Period (0-3 weeks)			Treatment Period (exenatide or albiglutide) (8 weeks)										Un scheduled	Early Withdrawal	Follow-Up	
	-3 to -1	-1 ¹⁶		1	2 ¹⁶	3	4	5 ¹⁶			6	7	8 ¹⁶				
Study Week	-3 to -1	-3 to -5	-1	1	10±1	-	-	29±1	31±1	32±1	-	-	52±1	53±1			12
Study Day	-21 to -4	-3 to -5	-1	1	10±1	-	-	X ¹⁴	X ¹⁵								78-84±3
Study Visits	1		2	3	4								8	9			10
Study treatment administration training, (1 st dose & 1 st uptitration dose)																	
Study treatment administration				X	X	X	X		X		X	X		X			
In clinic meal			X	X	X			X	X	X			X	X			
Study medication compliance			X	X				X	X	X			X	X			

1. **Before randomization**, the investigator must review **all** inclusion and exclusion criteria to confirm subject's eligibility. If a subject no longer meets all of the eligibility criteria, **do not randomize the subject** and contact the Medical Monitor to discuss how to proceed (e.g., to determine if repeat testing is warranted).
2. For subjects taking OAM at screening only. At a minimum, two day washout for immediate release and at a minimum 4 day washout for extended release OAMs. See footnote 16. For information on restarting OAM refer to Section 6.9
3. A small meal will be provided 2 hrs prior to the EGG procedure (Section 7.3.1). A meal will also be provided post-procedure for both the EGG and GEBT.
4. The Day 1 (baseline) EGG is to be conducted before administration of study medication.
5. The EGG must be scheduled 3±1 days after the albiglutide dose. The morning dose of exenatide will be administered at clinic 1 hr (± 15 min) before the EGG or GEBT procedure.
6. Weight only
7. Details of full and brief physical examinations are provided in Section 7.4.3.
8. Only related to study participation SAEs
9. The GCSI-DD questionnaire will be completed after the standard AE questions have been answered.
10. Clinical chemistry, hematology, urinalysis and lipid assessments are described in Section 7.4.6. Lipids will be assessed at screening only.
11. Creatinine for eGFR only
12. Subjects will be provided with diet and exercise guidance (see Section 7.4.8) and instructed on self monitoring blood glucose at screening (See Section 7.4.9). Subject will be instructed to bring in their glucometers at each visit for review. Diet/exercise/SMBG reinforced at subsequent visits.
13. Informed consent for optional Genetic research should be obtained before collecting a sample.
14. On the morning of Day 1, after baseline EGG test, subjects will receive instructions and training on exenatide or albiglutide self administration and will be monitored by medical staff at the clinic during administration of the first dose. The first dose of will be administered after the baseline EGG procedure and before the post-procedure meal.
15. On Day 29 (± 1 day), study treatment will be uptitrated to 10 μ g twice daily exenatide or 50 mg once weekly albiglutide (see Section 6.3). Subjects will receive instructions and training on exenatide or albiglutide self administration and will be monitored by medical staff at the clinic during administration of the first dose.
16. Every effort should be made to schedule the procedures on the nominal visit day identified. However, in order to meet scheduling needs, subjects taking OAM can schedule Day-1 up to 3 days prior to Day 1 and the OAM stopped at least the day before the GEBT . For subjects treated with diet and exercise alone Day-1 can occur within 7 days prior to Day 1. The EGG and GEBT should not be scheduled on the same day.

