6.9. Treatment after the End of the Study

Investigational product will not be provided to subjects by GSK after the end of the study. In Part A, the last dose of exenatide will be in the morning before the GEBT on Day 5±1. In Part B, the last dose of exenatide will be in the morning before the GEBT of Week 8 Day 4±1. The last dose of albiglutide will be on Week 8 Day 1.

The investigator is responsible for ensuring that consideration has been given to the post-study care of the subject's T2DM. After the last dose of albiglutide or exenatide, the investigator will provide subjects with instructions of how to continue to treat their

T2DM after the end of the study. The half-life of his/her study treatment (albiglutide/exenatide) should be taken into consideration.

- The half-life of albiglutide is approximately 5 days, and significant therapeutic concentrations can persist for 3 to 4 weeks after discontinuation. The choice of other medicinal products and dose selection should be considered accordingly, as adverse reactions may continue and efficacy may, at least partly, persist until albiglutide levels decline.
- The half-life of exenatide is 2-3 hours.

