7.3. EGG and GEBT Test

GEBT and EGG measurements will be undertaken in the clinic and performed on separate days. Measurements for both Part A and Part B will be taken at the time points specified in the Time and Events Table in Section [7.1](#). Clinical visits for EGG and GEBT will have a visit window of ± 1 day and should be planned to avoid days of expected holidays, weekends and vacations.

- Albiglutide should be self-administered in the morning 3 ± 1 days before the EGG procedure.
- Exenatide should be self-administered twice daily. In the morning of each test day, subjects should be instructed NOT to self-administer exenatide at home. The morning dose of exenatide on the day of in-clinic test must be administered by the site staff. The dose of exenatide should be administered 1 hr ± 15 min prior to the start of the EGG or GEBT procedure. Every effort should be made to administer at the same pre-procedure time at each visit for the same subject.

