CV safety of antidiabetic therapy	
Albiglutide:
 
T2DM is associated with an elevated risk of CV disease. Global regulatory agencies require new antidiabetic therapies to demonstrate that the new therapy is not associated with an unacceptable increase in CV risk.
 
In the Phase 3 registration program, an independent Clinical Endpoint Committee prospectively adjudicated blinded CV events. The final CV meta-analysis showed no increased CV risk (MACE+ composed of CV death, MI, stroke, and hospitalization for unstable angina) with albiglutide versus all comparators (MACE+ hazard ratio = 1.00; 95% CI: 0.68, 1.49).
	
Subjects with clinically significant CV and/or cerebrovascular disease at any time before screening will be excluded from the study. Further details are provided in Section 5.2.
 
See albiglutide IB or exenatide PI

	
Exenatide
 
There have been no clinical studies establishing conclusive evidence of macrovascular risk reduction with exenatide.
	
Hepatotoxicity	
Albiglutide:
 
One subject in the Phase 3 clinical program developed a probable drug-induced liver injury with an asymptomatic elevation in ALT and total bilirubin, although the case had some atypical features and complicating factors.
 
Exenatide:
 
No pharmacokinetic study has been performed in patients with diagnosis of acute or chronic hepatic impairment. Because exenatide is cleared primarily by the kidney, hepatic dysfunction is not expected to affect blood concentrations of exenatide.
	
Routine liver safety laboratory evaluations will be conducted and specific withdrawal criteria for elevated liver function tests have been defined (See Section 5.5.1).
 
Risk communication via informed consent form for subjects

Risk of Clinical Significance	Data/Rationale for Risk	Mitigation Strategy
Investigational Product: (albiglutide (GSK716155) and exenatide (Byetta)) Additional Considerations		

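### Part B schedules no liver test between screening and Week 8, when albiglutide dosing is complete and exenatide dosing nearly so

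*Protocol*

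**What the plan says.** Protocol 7.1, Table 3, has one row for "Chemistry, hematology, urinalysis, lipids". In Part B it is marked at screening, Week 5, Week 8 and early withdrawal, with nothing at Day -1, Day 1, Week 2 or follow-up. Footnote 11, attached to the Week 5 mark, reads "Creatinine for eGFR only". ALT, AST and bilirubin belong to the chemistry panel in Table 4 (7.4.7), which goes to a central laboratory. No other section schedules them.

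On dosing, footnote 15 says that on Day 29 (±1) "study treatment will be uptitrated to" the higher dose. Section 6.9 says "The last dose of albiglutide will be on Week 8 Day 1" and "the last dose of exenatide will be in the morning before the GEBT of Week 8 Day 4±1". Section 7.3 says "Clinical visits for EGG and GEBT will have a visit window" of ±1 day, and footnote 5 adds "The EGG must be scheduled 3±1 days after the albiglutide dose".

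On liver safety, 5.5, 5.5.1 and Appendix 5 set three kinds of rule:
- immediate stopping, for example at ALT of 8xULN or more, or at 3xULN or more with raised bilirubin or with symptoms believed liver-related;
- stopping after 2 weeks of ALT at 5 to 8xULN;
- stopping after 4 weeks of ALT at 3 to 5xULN.

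Below those limits, a subject with raised ALT may continue with weekly repeat tests. Appendix 2 gives the mitigation for hepatotoxicity as: "Routine liver safety laboratory evaluations will be conducted and specific withdrawal criteria for elevated liver function tests have been defined".

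**The concern.** Every Appendix 5 rule needs a first abnormal ALT, and the rules that stop or monitor therapy are useful only if that value is found while there are doses left to withhold. The Part B schedule hardly allows this: a symptom-free rise would not be seen until dosing is over or nearly over.

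Two features make the gap worth attention. First, entry permits ALT up to 2.5xULN and stable chronic liver disease (5.2), so some subjects may start close to the 3xULN threshold. Second, symptom-driven testing is a weak backstop here. Appendix 5 lists nausea and vomiting among liver symptoms, and these are the expected effects of both drugs, so they are easily put down to the drug's ordinary action.

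The kidney is treated differently. Creatinine is drawn at Week 5, where a result can still act on the withdrawal rule for eGFR below 60 (5.5). The liver has withdrawal rules but no matching test.

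**Working it through.** **Calendar.** Study Day = 7 x (week - 1) + day, with no Day 0 (SAP 9.2.1).
- Week 5 Day 1 = 29 and Week 8 Day 4 = 53. Both reproduce the days printed in Table 3.
- Week 8 Day 1 = 50, the last albiglutide dose.
- Last exenatide dose: morning of Day 53±1, so Days 52 to 54.
- Week 8 draw: Table 3's columns are shifted in the extracted text. The mark shares a column with the Week 8 EGG, which points to Visit 8 (Day 52±1). If it belongs to Visit 9, it is Day 53±1. The full range is Days 51 to 54.

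**Gap without a scheduled liver test.**
- Nominal: Day -4 to Day 52 = 52 + 4 - 1 = 55 days; Day -21 to Day 53 = 53 + 21 - 1 = 73 days.
- With windows: 51 + 4 - 1 = 54 and 54 + 21 - 1 = 74 days.

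**Albiglutide.** Doses fall on Days 1, 8, 15, 22, 29, 36, 43 and 50, which is 8 doses, all before the draw. Under footnote 5 an EGG-day draw comes 2 to 4 days after the dose. A Day 51 EGG-day draw is therefore not permitted after a Day 50 dose, and the order holds in every permitted case.

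**Exenatide doses left at the Week 8 draw** (two doses assumed on Day 1, draw taken before the morning dose):

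| Draw | Last dose | Doses left | Total doses |
|---|---|---|---|
| Day 52 | Day 53 | 2 + 1 = 3 | 2 x 52 + 1 = 105 |
| Day 53 | Day 53 | 1 | 105 |
| Day 51 | Day 54 | 2 + 2 + 2 + 1 = 7 | 2 x 53 + 1 = 107 |

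The largest gap from draw to last dose is 54 - 51 = 3 days. The order of EGG and GEBT is not fixed, so the draw can also follow the last dose by a day (Day 53 against Day 52). The documents give no laboratory turnaround. If it is 1 day, 0 to 1 dose remains nominally and at most 5 at the extreme. At 2 days the most is 3, and at 3 days it is 1.

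**What a Week 5 liver test could spare.** Inputs: draw on Day 29 or 31 (the column is again uncertain), nominal last doses, turnaround assumed to be 1 to 3 days.

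| Rule | Earliest action | Latest action | Albiglutide doses spared | Exenatide doses spared |
|---|---|---|---|---|
| Immediate stop | 29 + 1 = Day 30 | 31 + 3 = Day 34 | 3 (Days 36, 43, 50) | 23 x 2 + 1 = 47 down to 19 x 2 + 1 = 39 |
| 2-week persistence | 29 + 14 + 1 = Day 44 | 31 + 14 + 3 = Day 48 | 1 (Day 50) | 9 x 2 + 1 = 19 down to 5 x 2 + 1 = 11 |
| 4-week persistence | 29 + 28 = Day 57 | 31 + 28 = Day 59 | 0 | 0 |

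The 4-week dates are before any turnaround and already fall after Day 54. With the fix, the gap from screening to the next ALT becomes 29 + 4 - 1 = 32 to 31 + 21 - 1 = 51 days (31 to 52 with windows).

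**The case against.** **The risk is small.** Both drugs are marketed and given at approved doses. Appendix 2 cites one probable liver-injury case, with atypical features, in the albiglutide Phase 3 program, and 4.6 cites over 4000 subject-years of exposure. Part B would add about 31 x 8/52 = 4.8 albiglutide subject-years, so on that crude rate about 4.8/4000 = 0.001 comparable cases. The figure is rough: the Phase 3 share of the 4000 is not stated and milder ALT rises are not counted. The conclusion of low risk stands.

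**A reader might infer that the schedule contradicts Appendix 2.** It does not. Appendix 2 promises routine liver tests and withdrawal criteria. It does not promise a test while doses remain, and the screening, Week 8 and early-withdrawal panels satisfy its wording.

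**A reader might also infer that the Week 8 draw misses drug exposure.** For albiglutide it does the reverse. With a Tmax of about 3 days (2.1) and concentrations that can persist 3 to 4 weeks (6.9), a Day 52 or 53 draw falls near peak after the fourth 50 mg dose. Clinically significant abnormal values are then repeated under 7.4.7, and liver events are monitored under Appendix 5. What is lost is the chance to withhold doses, not the detection of a late abnormality.

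**The early-withdrawal panel does not close the gap.** It gives a subject who leaves a liver test, but dosing has already ended by then (5.5). During dosing only unscheduled or symptom-driven tests can act.

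**The remedy is limited.** Up-titration falls on Day 29±1, so Week 5 mainly reflects 30 mg or 5 µg. A symptom-free rise caused by the higher dose would still first appear at Week 8. This stands. It limits the benefit but does not remove it.

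**Conclusion.** The gap is real. For subjects who stay on treatment, scheduled testing cannot withhold any of the 8 albiglutide doses. It could withhold at most a few of about 105 exenatide doses, and nominally 0 or 1 once a 1-day turnaround is allowed. The albiglutide conclusion needs no turnaround assumption and holds whichever Week 8 visit carries the mark.

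The value of a Week 5 test depends on the rule met: up to three albiglutide doses under an immediate-stop criterion, about one under the 2-week rule, none under the 4-week rule. It would be wrong to read the three-dose figure as the general benefit. A symptom-free subject at 3 to 5xULN would continue dosing, and the gain would be weekly repeats that could show progression. The exenatide counts rest on the assumed turnaround and on the uncertain Week 5 column.

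This is worth fixing because the repair is cheap, not because the expected harm is large. The SAP reports that the study ended early in Part A, so the point concerns Part B as written.

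**What to change.** Change footnote 11 to read: *Creatinine for eGFR, ALT, AST, total and direct bilirubin*. Run these on the Week 5 sample already drawn, and leave the Appendix 5 thresholds and actions unchanged.

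**Cost.** One footnote and a small assay charge for up to about 62 subjects, with no new visit and no new blood draw.

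**Downsides.**
- Subjects with ALT of 3xULN or more would need weekly repeat tests.
- A subject with ALT of 3xULN or more and symptoms judged liver-related must stop treatment, and nausea is one of the listed examples. Stopping means leaving the study, and Part B does not replace withdrawals (5.5), so the trial could lose a nauseated subject of the kind it wants to measure.

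**What it leaves open.** Catching a rise caused by the higher dose while doses remain would need a new visit in Weeks 6 to 7, which the low expected risk does not clearly justify. Because albiglutide clears slowly, skipping late doses also lowers exposure only gradually.
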